## 8. SUBJECT ENROLLMENT

Before subjects begin participation in any study-specific activities and procedures, Amgen requires a copy of the site's written institutional review board or independent ethics committee (IRB/IEC) approval of the protocol, informed consent form, and all other subject information and/or recruitment material, if applicable (see Section 14.2). All subjects and/or legally acceptable representatives must personally sign and date the informed consent form before commencement of study-specific activities/procedures. A subject is considered enrolled when study entry criteria are met. The investigator (or designee) will document the enrollment decision and date in the screening log, subject's medical record and in the enrollment case report form (CRF).

Each subject who enters into the screening period for the study (defined as the time at which the subject signs the informed consent) receives a unique subject identification number before any study procedures are performed. The subject identification number will be assigned manually. The subject identification number must remain constant throughout the entire clinical study; it must not be changed after initial assignment.

The unique subject identification number will consist of 11 digits. The first 3 digits will represent the last 3 digits of the protocol number (ie, 544). The next 5 digits will represent the country code and site number (eg, 66001) and will be identical for all subjects at the site. The next 3 digits will be assigned in sequential order as subjects are screened (eg, 001, 002, 003). To illustrate, the first subject to enter screening at site 66001 will receive the number 54466001001. This number will be used to identify the subject throughout the clinical study and must be used on all study documentation related to that subject.

Subjects who do not meet the eligibility criteria within the 28-day screening period will not be eligible for enrollment. Subjects may be re-screened up to 3 times upon discussion with and approval by the Amgen Medical Monitor. The subject must be re-consented if a re-screen occurs outside the 28-day screening period. Re-screen subjects will repeat all screening procedures.

Subjects not meeting study entry criteria will be documented as screen failures.

Subjects may be eligible to begin treatment once all screening tests and procedures are completed and results indicate that all eligibility criteria are met. A site representative will complete and send the enrollment eligibility worksheet to the sponsor or designee.

---

The Amgen representative will acknowledge receipt and send confirmation of cohort, dose level assignment, and randomization number.

#### **8.1 Randomization/Treatment Assignment**

An Amgen representative will notify the site(s) in writing when a cohort is open to screen new subjects. As of Amendment 6, enrollment in Cohorts 1 to 8 is closed. There were no safety concerns noted that would preclude enrollment into the higher dose cohorts, 8 and 9.

On day -1 for cohorts 1 to 5 or day -3 to -1 for cohorts 6 to 9 (or up to day 1), eligible and enrolled subjects will be randomized to a treatment assignment in a double-blind fashion. Within each cohort, subjects will be randomly assigned in a 3:1 ratio to receive either AMG 890 or placebo. They will be assigned a randomization number based in sequential order in which they qualified to be randomized. Subjects will be considered randomized once a unique subject randomization number has been assigned. For cohorts 1 to 5, dosing should occur within 24 hours of randomization; for cohorts 6 to 9, dosing should occur within 3 days ( $\leq$  72 hrs) of randomization. If dosing cannot occur within the window for randomization, the Medical Monitor may be contacted to approve dosing outside the window (up to an additional 24 hours after randomization). The randomization date is to be documented in the subject's medical record and enrollment eCRF.

For cohorts 1 to 5, and cohort 9, the first 2 subjects (sentinel pair) will be randomized. One subject will receive AMG 890 and 1 subject will receive placebo. Subjects will be monitored for at least 24 hours before the remaining subjects in the cohort are dosed. Remaining subjects may be subsequently dosed provided there are no safety or tolerability concerns as assessed by the Principal Investigator.

For cohorts 6 to 9, at least 6 subjects in each cohort will be on a stable statin for 6 weeks prior to enrollment. Randomization in cohorts 6 to 8 will not use a sentinel dosing strategy. For cohorts 6 and 7, once 6 subjects not on a stable dose of statin are enrolled into cohort 6, then 6 subjects not on a stable dose of statin may be enrolled into cohort 7. Similarly, once 6 subjects on a stable dose of a statin are enrolled into cohort 6, then 6 subjects on a stable dose of a statin may be enrolled into cohort 7.

Enrollment in cohort 8 is closed, supported by the approval to dose escalate to the 225 mg dose of cohort 5 after the DLRT found that the previous dose regimen in cohorts

---

1 to 4 was safe and reasonably tolerated. In addition, the dose in cohort 5 was well tolerated with no safety signals observed in low Lp(a) level subjects.

Cohort 9 may be enrolled concurrently with cohort 8 or after cohort 8 has completed enrollment. If cohort 9 and cohort 8 are fully enrolled and there are additional subjects who have passed screening visit procedures, these subjects may be allowed to be enrolled and randomized in cohort 9 with approval of Amgen.

Amgen will provide a randomization schedule to the unblinded pharmacist at the site. The unblinded pharmacist will prepare all treatments accordingly. Subjects randomization will occur in accordance with the randomization schedule.

## **8.2 Site Personnel Access to Individual Treatment Assignments**

The subjects and the investigative site staff, except for the unblinded pharmacist, will be blinded to treatment assignment.

A subject's treatment assignment should only be unblinded when knowledge of the treatment is essential for the further management of the subject which may potentially impact the safety of subjects currently enrolled or subjects in subsequent cohorts.

Unblinding at the study site for any other reason will be considered a protocol deviation. The investigator is strongly encouraged to contact the Amgen Study Manager before unblinding any subject's treatment assignment, but must do so, in writing, within 1 working day after the event.

Treatment assignments will be unblinded after final database lock. After final database lock and receipt of written authorization from Amgen to unblind, the unblinded pharmacist will release the specified unblinded pharmacy records to site staff designated to enter the subject treatment into each subject's Unblinded Investigational Product Administration CRF.

## **9. TREATMENT PROCEDURES**

### **9.1 Classification of Product(s), Medical Device(s), and/or Combination Product(s)**

The Amgen Investigational Product(s) used in this study include: AMG 890 and placebo.

The Investigational Product Instruction Manual (IPIM), a document external to this protocol, contains detailed information regarding the storage, preparation, destruction, and administration of AMG 890 and placebo.

## 9.2                   Investigational Product

All investigational product(s) will be administered at the research facility by the investigator or designate.

A physician must be immediately available at the time of administration of Investigational Product in case of complication(s).

### 9.2.1               Amgen Investigational Product

AMG 890 will be distributed using Amgen clinical study drug distribution procedures. For cohorts 1 to 7, AMG 890 will be provided in a 6 mL sterile vial filled with 1 mL deliverable volume of 150 mg/mL AMG 890. For cohorts 8 and 9, AMG 890 will be provided in a 2 mL sterile vial filled with 1 mL deliverable volume of 75 mg/mL AMG 890.

For cohorts 1 to 7, placebo will be presented in 5 mL sterile vials filled with 1 mL deliverable volume; for cohorts 8 and 9, placebo will be provided in 2 mL sterile vials filled with 1 mL deliverable volume. Placebo will be stored under the same conditions as AMG 890.

### 9.2.2               Dosage, Administration, and Schedule

Subjects will receive AMG 890 or volume-matched placebo, respectively, via blinded SC injection in the abdomen according to the Schedule of Assessments (SOA) ([Table 4](#), [Table 5](#), [Table 6](#), [Table 7](#), [Table 8](#), and [Table 9](#)). AMG 890 administration time should be chosen carefully to avoid any interference or inconvenience with time point of safety assessments or PK/PD measurements.

For cohorts 1 to 5, and the sentinel pair of cohort 9, subjects will be admitted to the clinical site on day –1. Subject residency is approximately 5 days for cohorts 1 to 5, and is approximately 3 days for the sentinel pair of cohort 9. Cohorts 6 to 9 (other than the sentinel pair) will report to the clinical site on day 1 and will not have a required residency period. At the Investigator's discretion, subjects may stay at the clinic overnight from the check-in visit and/or day 1 for subject's convenience. Subjects will be randomized in a 3:1 ratio to receive AMG 890 or placebo, respectively, via SC injection, according to the Schedule of Assessments ([Table 4](#) to [Table 9](#)).

A single dose will be administered on day 1 following all required pre-dose procedures and confirmation of enrollment eligibility. For cohorts 1 to 5, and cohort 9, subjects will be dosed in a staggered fashion where 2 subjects will be dosed initially (randomized to AMG 890 or placebo in a 1:1 ratio), followed by the remaining subjects after a minimum of 24 hours and provided there are no safety or tolerability concerns as assessed by the

principal investigator. For cohorts 6 to 8, subjects may be dosed concurrently (see Section 8.1 for details).

The planned dose levels are, in milligrams (mg): 3, 9, 30, 75, 225 and 675.

Across all cohorts, the date, time, package lot number, and quantity administered are to be recorded on the individual subject's Investigational Product Administration eCRF prior to database lock.

The Investigator or study physician must be available when the subject receives the initial dose of AMG 890 for immediate intervention in case of complication(s). The subject's residency may be extended at the discretion of the investigator. During the residency periods, an immediately accessible emergency room with resuscitation equipment must be available.

Prior to discharge, clinical assessments per SOA ([Table 4](#) to [Table 9](#)) will be completed.

### **9.2.3 Dosing Error**

The effects of overdose/underdose of this product are not known. In case of dosing error, consultation with the Amgen medical monitor as soon as possible is recommended to discuss subject management and prompt reporting of clinically apparent or laboratory adverse events possibly related to the dosing error. Subjects should be monitored closely until symptom resolution. Adverse events should be reported and documented according to instructions available in Section 12.

### **9.2.4 Dose-cohort Study Escalation and Stopping Rules**

The planned doses of AMG 890 are shown in [Table 1](#).

The dosing schedule is described by the Schema in the Protocol Synopsis.

#### **9.2.4.1 Dose Level Review Meetings**

Dose level review meetings will be held to review subject data and monitor safety before escalation to the next higher dose cohort. The DLRT members will be composed of the investigators actively enrolling subjects at the time of the meeting (ie, have subjects in screening or already enrolled), the unblinded Amgen Medical Monitor, Amgen Global Safety Officer (GSO) or designated safety scientist, Clinical Study Manager, and Biostatistics representative. Additional members may be added as needed (eg, clinical pharmacologist). The DLRT voting members will include the investigator(s), Amgen Medical Monitor and Amgen GSO or designees. The DLRT is responsible for dosing recommendations, which may include escalation to the next planned dose, escalation to

an intermediate dose (a dose lower than the next planned dose), de-escalation to a lower dose; continuation, delay, or termination of dosing; or repetition or expansion of a cohort. Clear stopping rules will be followed, and ad hoc DLRMs will be held if necessary. All available study data, including demographics, medical history, concomitant medications, adverse events, electrocardiograms (if applicable), vital signs, and clinical laboratory test results will be reviewed. If available, emerging PK and PD data may also be reviewed in a manner that does not unblind individual treatment assignments.

Except for the unblinded Amgen Medical Monitor who will review data on an ongoing basis throughout the duration of study in an unblinded manner, data will be reviewed blinded (ie, treatment assignment will not be revealed) unless unblinding is deemed necessary for the review team to make dosing decisions. If deemed necessary, unblinding will be performed to assist dose change recommendations.

Investigators who are not actively enrolling subjects at the time of the DLRM will not participate in the DLRM. They will be informed of the decisions of the DLRT.

For cohorts 1 to 5, and cohort 9, escalation to a higher dose cohort will only proceed when the previous dose regimen has been found to be safe and reasonably tolerated based on available safety data through study day 15 for all subjects and upon unanimous recommendation of the DLRT. Available data from previous cohorts will also be considered. The next cohort will be open for enrollment immediately following the DLRT recommendation and Amgen decision.

Enrollment into cohorts 6 to 8 will be initiated after cohort 4 dose level has been found by the DLRT to be safe and reasonably tolerated based on available safety data through study day 15. Cohorts 5, 6 and 7 may be enrolled in parallel. For cohorts 6 and 7, eligible subjects will be first enrolled into cohort 6 and then into cohort 7. Cohort 8 will be enrolled after implementation of this protocol amendment. Enrollment into cohort 9 can be initiated after the preceding dose regimen has been found by the DLRT to be safe and reasonably tolerated based on available safety data through at least study day 15 of cohort 5. See Section [8.1](#) for details.

The planned dose escalation schedule may be modified based on treatment-emergent data (safety and/or PD). Dose adjustments, if any, will be made by Amgen on a treatment cohort and not on an individual basis.

The review of available safety data and dosing change decisions will be documented in meeting minutes. Amgen will issue a written notification of a dose change decision to investigators.

#### **9.2.4.2 Dose Stopping Rules**

Determination of the severity of adverse events will be as follows: mild (aware of sign or symptom, but easily tolerated), moderate (discomfort enough to cause interference with usual activity), and severe (incapacitating with inability to work or do usual activity).

Recommendations will be made by the DLRT to stop or modify dosing if suspected adverse drug reactions and/or changes in safety data (including but not limited to vital signs, electrocardiogram (ECG), or clinical laboratory results) are observed and these changes pose a significant health risk. The unblinded Amgen Medical Monitor will review data in an unblinded manner on an ongoing basis, and may suspend dosing and convene a DLRM at any time based on emerging safety data. In addition, dose escalation will be stopped or modified as shown in [Table 3](#).

Clinically or medically significant suspected adverse drug reactions, and serious adverse events considered to be related to study procedures will be followed until resolved or considered stable.

Administration of any drug by any route can cause anaphylaxis. Anaphylaxis is a life-threatening medical emergency in which prompt intervention is critical. Therefore, in the case of a suspected event, monitoring, preferably continuous hemodynamic monitoring, is essential. Monitoring should include blood pressure, continuous pulse rate, pulse oximetry, and electrocardiographic monitoring. Intravenous access should be obtained as soon as possible. These measures should be used to monitor response to therapy and direct subsequent interventions. The decision to initiate specific treatment for anaphylaxis, which may include the prompt administration of parenteral epinephrine, requires clinical judgment, should not be delayed by other procedures, and should follow the World Allergy Organization Anaphylaxis Guidelines (Ronna et al, 2014) or the local institutional practices.

Any subject with suspected anaphylactic reaction should be evaluated using the clinical criteria for diagnosis of anaphylaxis below (Sampson et al, 2006). If the criteria for anaphylaxis is met, a blood tryptase test must be collected as soon as the effective treatment has been rendered. Treatment administration for a suspected anaphylaxis event should not be delayed by any clinical or laboratory test collection. The event and

---

test results should be documented in the subject's medical record and reported as an adverse event as appropriate (Section 12).

**Anaphylaxis is highly likely when any one of the following 3 criteria are fulfilled:**

1. Acute onset of an illness (minutes to several hours) with involvement of the skin, mucosa, or both (eg, generalized hives, pruritus or flushing, swollen lips-tongue-uvula), and at least 1 of the following
  - a. Respiratory compromise (eg, dyspnea, wheeze-bronchospasm, stridor, reduced peak expiratory flow [PEF], hypoxemia)
  - b. Reduced blood pressure (BP) or associated symptoms of end-organ dysfunction (eg, hypotonia [collapse], syncope, incontinence)
2. Two or more of the following that occur rapidly after exposure to a likely allergen (minutes to several hours):
  - c. Involvement of the skin or mucosa (eg, generalized hives, itch, swollen lips-tongue-uvula)
  - d. Respiratory compromise (eg, dyspnea, bronchospasm, stridor, reduced PEF, hypoxemia)
  - e. Reduced BP or associated symptoms (eg, hypotonia [collapse], syncope, incontinence)
  - f. Persistent gastrointestinal symptoms (eg, crampy abdominal pain, vomiting)
3. Reduced BP after exposure to an allergen (minutes to several hours):
  - g. Systolic BP < 90 mmHg or greater than 30% decrease from that person's baseline

**Table 3. Cohort Dose Stopping Rules**

| Scenario  | Action  |
|---|---|
| Any occurrence of a suspected adverse drug reaction classified as moderate in 2 or more subjects in the same cohort | 

Stop dosing additional subjects and convene DLRM (if event occurs outside of the regularly scheduled DLRM)

Review adverse event and all relevant safety data for evidence of relationship to treatment and clinical or medical significance

Consider unblinding as appropriate

Upon unanimous decision by the DLRT members, 1 of the following recommendations may be made:

stop enrollment of the cohort (if applicable)

resume enrollment of the cohort as planned

resume enrollment of the cohort at a lower dose

expand the cohort at the same dose

add a lower dose cohort to the study

escalate to an intermediate dose (a dose lower than the next planned dose)

escalate to the next planned dose

  |
| Any occurrence of a suspected adverse drug reaction classified as severe                                     | 

Stop dosing additional subjects and convene DLRM (if event occurs outside of the regularly scheduled DLRM)

Review adverse event and all relevant safety data for evidence of relationship to treatment and clinical or medical significance

Consider unblinding as appropriate

If the adverse event is determined by unanimous decision of the DLRT members to be related to study drug (after breaking of the study blind) and clinically or medically significant, no further doses should be administered at this dose and no dose escalation should proceed. Enrollment of the study may continue at a lower dose or a lower dose cohort may be added to the study.

Otherwise (ie, if considered not related to study drug or not clinically relevant), upon unanimous decision of the DLRT members, 1 of the following recommendations may be made:

resume enrollment of the cohort as planned

resume enrollment of the cohort at a lower dose

expand the cohort at the same dose

add a lower dose cohort to the study

escalate to an intermediate dose (a dose lower than the next planned dose)

escalate to the next planned dose

 |

 A subject's treatment assignment should only be unblinded when knowledge of the treatment is essential for the further management of the subject, or may impact the safety of subjects currently enrolled, or subjects in subsequent cohorts.

The Amgen Medical Monitor will be unblinded to treatment assignment throughout the duration of the study.

### 9.3 Other Protocol-required Therapies

For cohorts 6 to 9, at least 6 subjects in each cohort are required to be on a stable dose of the same statin through EOS as defined in subject eligibility (Section 7).

Specific product, dose and dosage regimen should be defined by subject's health care provider, based on the individual medical background. Subject must be on stable dose of the same drug for 6 weeks prior to enrollment.

For additional information, refer to the manufacturer package insert.

Information about therapy name, indication, dose, unit, frequency, route, start date, and stop date should be collected in the concomitant medication eCRF.

Protocol required therapies that are commercially available are not provided or reimbursed by Amgen (except if required by local regulation). The investigator will be responsible for obtaining supplies of these protocol-required therapies.

### 9.4 Hepatotoxicity Stopping and Rechallenge Rules

Subjects with abnormal hepatic laboratory values (ie, ALP, AST, ALT, TBIL) and/or international normalized ratio (INR) and/or signs/symptoms of hepatitis (as described below) may meet the criteria for withholding or permanent discontinuation of Amgen IP or other protocol-required therapies (as specified in the FDA Guidance for Industry Drug-induced Liver Injury: Premarketing Clinical Evaluation, July 2009).

#### 9.4.1 Criteria for Permanent Withholding of Amgen Investigational Product and Other Protocol-required Therapies due to Potential Hepatotoxicity

Investigational product and other protocol-required therapies, as appropriate, should be discontinued permanently and the subject should be followed according to the recommendation in the [Appendix A](#) (Additional Safety Assessment Information) for possible drug-induced liver injury (DILI), if ALL the criteria below are met:

- TBIL > 2x upper limit of normal (ULN) or INR > 1.5
- AND increased AST or ALT from the relevant baseline value as specified below:

| Baseline AST or ALT value | AST or ALT elevation |
|---------------------------|----------------------|
| < ULN                     | > 3x ULN             |

- AND no other cause for the combination of the above laboratory abnormalities is immediately apparent; important alternative causes for elevated AST/ALT and/or TBIL values include, but are not limited to:
  - Hepatobiliary tract disease
  - Viral hepatitis (eg, Hepatitis A/B/C/D/E, Epstein-Barr Virus, cytomegalovirus, herpes simplex virus, varicella, toxoplasmosis, and Parvovirus)
  - Right sided heart failure, hypotension or any cause of hypoxia to the liver causing ischemia.
  - Exposure to hepatotoxic agents/drugs or hepatotoxins, including herbal and dietary supplements, plants and mushrooms
  - Heritable disorders causing impaired glucuronidation (eg, Gilbert's Syndrome, Crigler-Najjar syndrome) and drugs that inhibit bilirubin glucuronidation (eg, indinavir, atazanavir)
  - Alpha-1 antitrypsin deficiency
  - Alcoholic hepatitis
  - Autoimmune hepatitis
  - Wilson's disease and hemochromatosis
  - Nonalcoholic Fatty Liver Disease including Steatohepatitis (NASH)
  - Non-hepatic causes (eg, rhabdomylosis, hemolysis)

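### One liver case meeting Section 9.4.1, or one serious suspected reaction graded below severe, does not by rule pause dosing of the remaining cohort 9 subjects; one added row in Table 3 would close this gap

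*Protocol*

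**What the plan says.** Protocol Table 3 has two triggers. The first is "Any occurrence of a suspected adverse drug reaction classified as moderate in 2 or more subjects in the same cohort". The second is a single suspected reaction graded severe. The first action is the same for both: "Stop dosing additional subjects and convene DLRM (if event occurs outside of the regularly scheduled DLRM").

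Section 9.2.4.2 and Appendix A grade severity by function. The top grade is "severe (incapacitating with inability to work or do usual activity"), and moderate means discomfort that gets in the way of ordinary activity. Neither grade refers to a laboratory value or to seriousness.

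Section 9.4.1 covers possible drug-induced liver injury: bilirubin above 2x ULN or INR above 1.5, together with raised AST or ALT, and no other cause at hand. Its instruction is: "Investigational product and other protocol-required therapies, as appropriate, should be discontinued permanently and the subject should be followed". Appendix A adds a serious adverse event report within 24 hours and a period of close observation. Neither place mentions Table 3, a dose level review meeting, or the dosing of other subjects. Section 9.2.2 gives each subject one dose, on day 1.

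Other provisions also bear on dosing:

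- Section 9.2.4.2: "Recommendations will be made by the DLRT to stop or modify dosing if suspected adverse drug reactions and/or changes in safety data" (laboratory results are named among these) "are observed and these changes pose a significant health risk".
- Section 9.2.4.2, on the Medical Monitor, who "may suspend dosing and convene a DLRM at any time based on emerging safety data". The Table 3 footnote adds: "The Amgen Medical Monitor will be unblinded to treatment assignment throughout the duration of the study".
- Sections 8.1 and 9.2.2: after the cohort 9 sentinel pair, at least 24 hours must pass, and the rest are dosed only if the Principal Investigator sees no problem with safety or tolerability.
- Section 10.3, Physical Examination: clinical evidence of treatment-emergent neuropathy suspends dosing.

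**The concern.** Section 9.4 carries the word stopping in its title, but in a single-dose study it has no further AMG 890 to stop. It can still end a statin or another protocol-required therapy in the affected subject. The rule that does protect subjects not yet dosed is Table 3, and Table 3 looks only at functional grade. Serious liver injury is often first seen in laboratory values, before the subject feels ill, so the event for which the protocol has its most detailed subject-level rule may not reach its cohort-level rule. The same holds for one event that is serious under Section 12.1.2 but graded moderate.

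This matters now for cohort 9 only. Enrolment in cohorts 1 to 8 is closed, and cohort 9 receives 675 mg, the highest dose. What is at stake is whether subjects still waiting are dosed between the recognition of a first case and its review.

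**Working it through.** **Nearest stated figure.** The plan gives no number for this point. Protocol Section 13.2 states a 74% chance of seeing an event of 20% incidence among 6 active subjects: 1 − (1 − 0.20)^6 = 1 − 0.2621 = 0.738, which agrees. That is the chance of observing an event. It does not say what happens next.

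**The rules side by side**, for events in cohort 9:

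| Event | Table 3 | Other compulsory pause |
|---|---|---|
| One suspected reaction graded severe, including a liver case so graded | Fires | Not needed |
| Suspected reactions graded moderate in two subjects | Fires | Not needed |
| Treatment-emergent neuropathy | Depends on grade | Yes, Section 10.3 |
| One case meeting Section 9.4.1, without symptoms | Does not fire | None; Section 9.4.1 and Appendix A act on that subject |
| One serious suspected reaction graded mild or moderate | Does not fire | None; 24-hour report under Section 12.2.1.2 |

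The last two rows are the gap. Seriousness and severity are separate scales in this protocol. Section 12.1.2 gives drug-induced liver injury as an example of an event that may be serious on medical importance alone.

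**Timing.** The sentinel hold need last only 24 hours (Section 8.1). As Tables 8 and 9 read, early post-dose chemistry in cohort 9 is taken at 24 hours, 72 hours, day 7 and day 29. With the minimum hold, most early liver results from the sentinel subject come after the others may be dosed.

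**Illustration only.** The documents give no rate for such cases. Assume a rate p per active subject, independence and immediate detection, and ignore placebo cases. Cohort 9 has 6 active subjects (Table 1), one of them in the sentinel pair. A pause can spare an active subject only if a case falls in the first 5.

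- Dosed one at a time, chance of a case while an active subject is still undosed: 1 − (1 − p)^5.
- Chance that Table 3 as written fires in time if every case is graded moderate (at least 2 in the first 5): 1 − (1 − p)^5 − 5p(1 − p)^4.
- Other five active subjects dosed together after the sentinel: the relevant chance is p, and the moderate trigger cannot fire because only one active subject has gone before.

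| Assumed p | Case in time, one at a time | Table 3 fires in time, all moderate | Case in time, dosed together |
|---|---|---|---|
| 2% | 9.6% | 0.4% | 2% |
| 5% | 22.6% | 2.3% | 5% |
| 10% | 41.0% | 8.1% | 10% |

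These are ceilings. They ignore the delay before a case is known and any pause ordered on judgement. In the last column, the Principal Investigator's check covers the sentinel case once it is known. If every case were graded severe, Table 3 would already fire and a new row would add nothing.

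**The case against.** The strongest reply is that Table 3 is only part of the rule. Section 9.2.4.2 states the DLRT's duty first and introduces Table 3 as an addition to it. A case meeting Section 9.4.1 plainly fits the health-risk clause, reaches the sponsor within 24 hours and before the work-up is complete, and is seen by a Medical Monitor who knows the treatment and can suspend dosing. Section 9.2.4.1 allows ad hoc meetings. After the sentinel pair, the Principal Investigator must also be satisfied, and that check has no severity threshold. For dosing to continue, all of these people would have to let it. This stands, and it limits the weight of the point.

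A second reply is that the proposed row also needs judgement: whether another cause is apparent, whether a reaction is suspected, whether it is serious. That is true. The row fixes the consequence once the classification is made; it does not remove the classification.

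A third is that the assumed rates have no source and may be high. By plan, 54 active subjects come before cohort 9 (5 × 6 + 2 × 9 + 6), and the protocol reports no safety concern precluding cohorts 8 and 9. The chance of no case in 54 is 0.95^54 = 6.3% at a 5% rate and 0.90^54 = 0.3% at a 10% rate. Those doses were lower and the protocol does not say that there were no cases, but the upper end of the range does look implausible. Section 5.2.3 also describes the animal liver enzyme and bilirubin changes as minimal to mild and not adverse.

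Two stronger readings are tempting. A reader might infer that dosing would carry on after a liver case; the safeguards above do not support that. A reader might also infer from the single row of the Section 9.4.1 AST/ALT table that subjects with a raised baseline have no threshold. The table may be incomplete in the text available, and Appendix A provides a 2-fold rule for close observation of such subjects, so no point is made of it.

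**Conclusion.** The gap is real and narrow. A single symptom-free case meeting Section 9.4.1, or a single serious suspected reaction graded below severe, leads to a pause in cohort 9 only if someone decides on one. For neuropathy the protocol has already made that decision in advance, so a comparable rule for liver cases and serious reactions fits its own approach.

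This is a cheap safety improvement, not an error in the plan. The benefit is a guaranteed pause in place of a probable one, and the documents do not allow its size to be estimated. The percentages above rest on assumed rates and immediate detection, and should not be read as the risk that the new row would remove. The conclusion applies only while subjects in cohort 9 remain undosed.

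**What to change.** Add a third row to Protocol Table 3. The trigger is any case meeting the Section 9.4.1 criteria, or any suspected adverse drug reaction reported as serious, whatever its severity grade. The action is the existing first one, stopping further dosing and convening the DLRM. The DLRT then considers unblinding and chooses among the options already listed. Cross-reference the row in Section 9.4.1.

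No new assessment, subject or committee is needed. The cost is a protocol amendment, which under Section 15.1 needs IRB/IEC approval before a site can implement it, so it is best bundled with another change. Cohort 9 could finish dosing before it takes effect. Once in force, it would occasionally cause an extra meeting and a short pause for a case that proves to be on placebo or unrelated.
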